11.2.13. Safety Analyses

All analyses will depend on the analysis populations being specified. For the analyses and summary statistics, the 2 analysis populations to be used are randomized subject population and placebo-controlled population. The randomized subject population will include all randomized subjects in the A4 study and will include observations across both the placebo-controlled period and the open-label period. The placebo-controlled population will include all enrolled subjects who have entered the placebo-controlled period of the A4 study and will be limited to observations collected during the placebo-controlled period of the study.

Safety will be assessed by summarizing and analyzing AEs, laboratory analytes, vital signs, MRI scans, ECGs, immunogenicity measures, and the C-SSRS during the treatment period. Safety analyses of the open-label extension will span across both the placebo-controlled study period and the open-label study period in order to be able to compare early-start safety risks to early-start efficacy benefits.

For safety assessments, 3 separate sets of analyses will be conducted: 1 set of analyses for all data when the subjects were on 400 mg Q4W, 1 set of analyses for all data when the subjects were receiving doses higher than 400 mg Q4W, and 1 set of analyses for all data (regardless of dose).

11.2.13.1. Study Drug Infusion

Summary statistics will be provided for the total number of subjects who received complete infusions, duration of complete infusion, and volume of complete infusion by treatment group at each visit. The proportions of subjects who received complete infusion between treatments will be compared between treatment groups. Duration of complete infusion and volume of complete infusion will also be compared between treatment groups.

Frequencies and percentages of reasons why infusion was incomplete or not done will also be presented.

11.2.13.2. Adverse Events

Adverse events will be coded according to established Medical Dictionary for Regulatory Activities (MedDRA) terms and summarized by MedDRA System Organ Class and Preferred Term.

Treatment-emergent adverse events will be defined as events that first occurred or worsened on or after the first infusion.

An overview of AEs, including the number and percentage of subjects who died, suffered SAEs, discontinued due to AEs, and who suffered TEAEs, will be provided. Comparison between treatments will be performed.

Summaries of AEs by decreasing frequency of preferred term within system organ class will be provided for the following:

- Preexisting conditions
- TEAEs
- TEAEs by maximum severity
- TEAEs occurring in greater than 5% of subjects by Preferred Term
- SAEs

A summary of TEAEs by visit will also be provided.

In addition, the proportion of subjects within specific clusters of TEAEs, such as infusion-related reactions, hemorrhagic stroke and cerebral microhemorrhage, cardiac ischemia-related events, cardiac arrhythmia-related events, and suicidal ideation or behaviors will be summarized and treatment comparisons will be conducted.

Preexisting conditions, TEAEs, SAEs, and discontinuations due to AEs will be listed.

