7.13.1.4. Analyses of Specific Clusters of TEAEs

In addition, the proportion of participants within the following specific clusters of TEAEs will be summarized and treatment comparisons will be conducted using Fisher's exact test:

- infusion-related reactions including anaphylaxis and urticaria, overall and broken out by immediate (same day as infusion) versus delayed
- suicidal ideation or behaviors
- hemorrhagic stroke
- cardiac ischaemic events
- cardiac arrhythmias, and
- amyloid-related imaging abnormality – hemorrhage (ARIA-H, also known as microhemorrhage).

The listing of preferred terms of the TEAEs corresponding to each specific cluster above is provided in [Appendix 2](#).

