Appendix 2. List of Preferred Terms for Specific Clusters of TEAEs

Specific TEAE cluster	Preferred terms
Infusion-related reactions including anaphylaxis and urticaria	infusion related reaction procedural dizziness procedural headache procedural hypotension procedural nausea procedural hypertension anaphylactic reaction anaphylactic shock anaphylactic transfusion reaction anaphylactoid reaction anaphylactoid shock first use syndrome Kounis syndrome shock Type I hypersensitivity urticaria
Suicidal Ideation or Behaviors	completed suicide depression suicidal intentional overdose intentional self-injury multiple drug overdose intentional poisoning deliberate self-injurious behavior self-injurious ideation suicidal behavior suicidal ideation suicide attempt

Specific TEAE cluster	Preferred terms
Hemorrhagic Stroke	basal ganglia haemorrhage basal ganglia stroke brain stem haemorrhage brain stem stroke cerebellar haematoma cerebellar haemorrhage cerebral haematoma cerebral haemorrhage cerebrovascular accident cerebrovascular disorder haemorrhage intracranial haemorrhagic cerebral infarction haemorrhagic stroke haemorrhagic transformation stroke intracerebral haematoma evacuation intracranial haematoma intraventricular haemorrhage meningorrhagia putamen haemorrhage spinal cord haemorrhage spinal cord haematoma stroke in evolution subarachnoid haemorrhage thalamus haemorrhage

Specific TEAE cluster	Preferred terms

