	
 Electrocardiogram delta waves abnormal Electrocardiogram PQ interval prolonged Electrocardiogram PR prolongation Electrocardiogram PR shortened Electrocardiogram QRS complex prolonged Electrocardiogram QT prolonged Electrocardiogram repolarisation abnormality Lenegre's disease Long QT syndrome Nodal arrhythmia Nodal rhythm Sick sinus syndrome Sinoatrial block Sinus arrest Sinus arrhythmia Sinus bradycardia Trifascicular block Ventricular asystole Ventricular dyssynchrony Wandering pacemaker Wolff-Parkinson-White syndrome 
 
 Cardiac arrhythmia terms, nonspecific (SMQ) Arrhythmia Heart alternation Heart rate irregular Pacemaker generated arrhythmia Pacemaker syndrome Paroxysmal arrhythmia Pulseless electrical activity Reperfusion arrhythmia Withdrawal arrhythmia 
 
 Supraventricular tachyarrhythmias (SMQ) Arrhythmia supraventricular Atrial fibrillation Atrial flutter Atrial parasystole Atrial tachycardia Supraventricular extrasystoles Supraventricular tachyarrhythmia ECG P wave inverted Electrocardiogram P wave abnormal Retrograde p-waves Sinus tachycardia Supraventricular tachycardia 

Specific TEAE cluster	Preferred terms
	
Tachyarrhythmia terms, nonspecific (SMQ)
 
 Anomalous atrioventricular excitation Atrioventricular extrasystoles Cardiac flutter Extrasystoles Tachyarrhythmia 
Ventricular tachyarrhythmias (SMQ)
 
 Accelerated idioventricular rhythm Cardiac fibrillation Parasystole Rhythm idioventricular Torsade de pointes Ventricular arrhythmia Ventricular extrasystoles Ventricular fibrillation Ventricular flutter Ventricular parasystole Ventricular pre-excitation Ventricular tachyarrhythmia Ventricular tachycardia

Amyloid-related imaging abnormality – hemorrhage (ARIA-H, also known as microhemorrhage)
	
Amyloid related imaging abnormality-microhaemorrhages and haemosiderin deposits
 
 Brain stem microhaemorrhage Cerebral microhemorrhage Cerebellar microhemorrhage Cerebral haemorrhage Superficial siderosis of central nervous system Cerebral haemosiderin deposition

Abbreviations: ECG = electrocardiogram; TEAE = treatment-emergent adverse event.

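### The SAP's hemorrhagic-stroke cluster includes five stroke terms of unspecified type with no pooled row for named bleeds, and its microhemorrhage cluster includes cerebral haemorrhage

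*Protocol*

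**What the plan says.** Protocol section 11.2.13.2 commits to summarising and comparing "the proportion of subjects within specific clusters of TEAEs, such as infusion-related reactions, hemorrhagic stroke and cerebral microhemorrhage", along with other clusters. It gives no term lists.

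SAP section 7.13.1.4 makes hemorrhagic stroke and ARIA-H two separate clusters and fixes the test: "the proportion of participants within the following specific clusters of TEAEs will be summarized and treatment comparisons will be conducted using Fisher's exact test". For the content of each cluster it says only this: "The listing of preferred terms of the TEAEs corresponding to each specific cluster above is provided in" Appendix 2. SAP section 7.13 sets the level at two-sided 0.05 without multiplicity adjustment.

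In Appendix 2 the hemorrhagic-stroke list includes the runs "basal ganglia stroke brain stem haemorrhage brain stem stroke" and "cerebral haemorrhage cerebrovascular accident cerebrovascular disorder haemorrhage intracranial", and later "stroke in evolution". The ARIA-H list, whose label equates ARIA-H with microhemorrhage, includes "Cerebral haemorrhage". Neither list comes with a rationale, a narrow or broad designation, or an adjudication step.

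**The concern.** A cluster's name tells the reader what was counted. Here a participant whose only event is coded as a cerebrovascular accident enters the table as a hemorrhagic stroke, whether or not anyone established a bleed. Cerebrovascular disorder does not even name a stroke.

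Two things could go wrong. If strokes of unspecified type are mostly unrelated to treatment, they dilute a true excess of bleeds. If they happen to be imbalanced, the table shows a hemorrhagic-stroke signal that may contain few confirmed bleeds. No planned analysis pools only the terms that name a bleed, so the reader cannot tell which has happened from a planned test.

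The second issue is smaller. The AE-based microhemorrhage row would include cerebral haemorrhage, a term that says nothing about a small lesion and that the plan also counts as hemorrhagic stroke.

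Bleeding matters in this trial. The Protocol's Introduction names ARIA-H as a potential risk of amyloid-directed therapies, and the dose was raised during the study.

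**Working it through.** The documents state no event rate, power or count for these clusters, so there is no planned figure to reproduce.

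**Step 1: count the terms (SAP Appendix 2).**
- Hemorrhagic stroke: 24 terms. Those with no wording for haemorrhage, haematoma or meningorrhagia are basal ganglia stroke, brain stem stroke, cerebrovascular accident, cerebrovascular disorder and stroke in evolution. That is 5/24 = 21%, which leaves 24 − 5 = 19 named-bleed terms.
- ARIA-H: 7 terms. One of them, cerebral haemorrhage, is also on the stroke list. Without it, 7 − 1 = 6 terms remain and the two lists no longer overlap.

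**Step 2: compare with the Protocol.** Section 10.2.12 lists hemorrhagic stroke and microhemorrhage as separate items for safety monitoring. It spells out microhemorrhage by site as cerebral, cerebellar or brain stem. Cerebral haemorrhage is not among these. Section 8.4.1 also distinguishes ischemic from hemorrhagic cerebral events.

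**Step 3: illustrate the effect on the test.** From the documents: about 575 per arm (SAP section 6.1), Fisher's exact test and two-sided 0.05. All rates below are assumptions. Exact power is

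power = Σᵢ Σⱼ b(i; 575, p₀) · b(j; 575, p₁) · 1[Fisher p(i, j) ≤ 0.05],

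where b is the binomial probability. For true bleeds take p₀ = 0.5% and p₁ = 2.0%, which is about 2.9 versus 11.5 expected participants.

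*Dilution of the broad list.* Add the same proportion u of unrelated strokes to both arms, so the risk ratio is (2.0% + u)/(0.5% + u):

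| u | Risk ratio | Power |
|---|---|---|
| 0 | 4.0 | 55% |
| 0.25% | 2.25/0.75 = 3.0 | 47% |
| 0.5% | 2.5/1.0 = 2.5 | 41% |
| 1% | 3.0/1.5 = 2.0 | 34% |
| 2% | 4.0/2.5 = 1.6 | 25% |
| 4% | 6.0/4.5 = 1.33 | 17% |

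*Loss in a narrow list.* Suppose a fraction m of true bleeds is coded to one of the five unspecified terms, so the narrow rates are (1 − m) times the true rates:

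| m | Narrow rates | Power |
|---|---|---|
| 30% | 0.35% vs 1.40% | 36% |
| 40% | 0.30% vs 1.20% | 29% |

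With true bleeds of 1.0% versus 3.0% the pattern is the same. Power is 62% for true bleeds and 46-26% with 1-4% of unrelated strokes added. It is 44% for the narrow list with 30% of bleeds coded as unspecified.

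Losing 30% of bleeds from the narrow list costs about as much power (36%) as adding 1% of unrelated strokes to the broad one (34%). Neither list is better at all plausible rates.

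**The case against.** The strongest reply is that the list is deliberately broad. The five terms leave the type open; they do not exclude a bleed. The list contains no term that names an ischaemic, embolic or thrombotic stroke, which fits a sensitive search that keeps any stroke that might have bled. This stands. A reader might infer that the cluster mixes in strokes known to be non-haemorrhagic, but Appendix 2 does not show that. What remains is that the SAP neither says the search is broad nor labels the result that way.

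Second, a reader might conclude that the narrow list should become the only hemorrhagic-stroke result. The second table above is against this: bleeds recorded without a type would drop out.

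Third, the overlap of cerebral haemorrhage can look like double counting. Each cluster is tested separately and they are never summed, so no single test counts a participant twice. Overlap also occurs elsewhere in Appendix 2, where Kounis syndrome is in both the infusion-reaction and the cardiac-ischaemia lists. The ARIA-H list already goes beyond microhemorrhage by including superficial siderosis, and cerebral haemorrhage is a bleed whose size the term does not state. The objection to it is therefore one of labelling and of consistency with Protocol section 10.2.12.

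Fourth, other analyses help. SAP section 7.13.1.1 tabulates and tests events by single preferred term, and SAP section 7.13.5 compares ARIA-H from MRI. These mitigate the problem only in part. Single-term rows scatter rare bleeds over 19 terms, which is what a cluster is meant to overcome. The MRI analysis does not address the stroke cluster. It also will not match the AE-based ARIA-H row, because Protocol section 10.2.1.1 requires only symptomatic ARIA to be reported as an adverse event.

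**Conclusion.** The point holds as one of labelling and a missing row. As written, the SAP reports strokes of unspecified type as hemorrhagic through 5 of 24 terms, plans no pooled comparison of named bleeds, and places cerebral haemorrhage in a cluster labelled microhemorrhage.

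The size cannot be fixed from the documents. With 575 per arm and assumed true rates of 0.5% versus 2.0%, power of 55% falls to 47-17% in the broad list. This assumes that the added strokes (0.25-4%) are unrelated to treatment, equally frequent in both arms, and never haemorrhagic. The narrow list has 36-29% if 30-40% of true bleeds are coded as unspecified. These ranges support showing both rows and do not favour either alone. The primary efficacy result is unaffected, and the preferred-term tables and the MRI analysis limit the harm.

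**What to change.** In SAP Appendix 2 and the tables under section 7.13.1.4:

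1. Keep the 24-term list and relabel it hemorrhagic or type-unspecified stroke (broad).
2. Add a narrow row of the 19 terms that name haemorrhage, haematoma or meningorrhagia, and a row for the five unspecified terms. Apply the same Fisher test to each and show the three rows together, with neither the broad nor the narrow row as the sole result.
3. In the ARIA-H cluster, report the six microhemorrhage, siderosis and haemosiderin terms together and show cerebral haemorrhage as its own row. It stays in the stroke lists.

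The cost is an appendix edit and a few table rows, with no new data and no change to study conduct. The downsides are extra unadjusted comparisons and a narrow row that misses bleeds coded as unspecified; those events remain visible in the other two rows. A bleed coded as cerebral haemorrhage leaves the pooled ARIA-H figure but can be read directly beside it.

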11.2.13.3. Laboratory Analyses

Laboratory measurements will be analyzed using continuous data (change from baseline) and categorical data (proportion of treatment-emergent abnormalities).

11.2.13.4. Electrocardiograms

The ECG measurements will be analyzed using continuous data (change from baseline) and categorical data (proportion of treatment-emergent abnormalities).

11.2.13.5. Vital Signs

Vital sign measurements (including temperature and weight) will be analyzed using continuous data (change from baseline) and categorical data (proportion of treatment-emergent abnormalities).

11.2.13.6. Immunogenicity

Immunogenicity data (anti-solanezumab) after treatment will be compared between the treatment groups.

11.2.13.7. Amyloid-Related Imaging Abnormalities: Magnetic Resonance Imaging

The incidence of ARIA-E will be summarized. Change in ARIA-E status from baseline, to each postbaseline MRI will be compared between treatment groups.

The incidence of ARIA-H will be summarized. Change in ARIA-H status from baseline to each postbaseline MRI will be compared between treatment groups.

11.2.13.8. Columbia Suicide Severity Rating Scale

Suicidal ideation, suicidal behavior, and self-injurious behavior without suicidal intent occurring during treatment, based on the C-SSRS, will be summarized. In particular, for each of the following events, the number and percentage of patients with the event will be enumerated by treatment: completed suicide, nonfatal suicide attempt, interrupted attempt, aborted attempt, preparatory acts or behavior, active suicidal ideation with specific plan and intent, active suicidal ideation with some intent to act without specific plan, active suicidal ideation with any methods (no plan) without intent to act, nonspecific active suicidal thoughts, wish to be dead, and self-injurious behavior without suicidal intent.

Results will be summarized for “at any time” (irrespective of baseline) and “treatment emergent” (new or worsening since baseline) events.

In addition, the number and percentage of patients who experienced at least 1 component of various composite measures will be presented. Composite endpoints are defined below.

- Suicidal ideation: A “yes” answer at any time during treatment to any 1 of the 5 suicidal ideation questions on the C-SSRS.
- Suicidal behavior: A “yes” answer at any time during treatment to any 1 of the 5 suicidal behavior questions on the C-SSRS.

11.2.14. Subgroup Analyses

To assess the effects of various demographic and baseline characteristics, subgroup analyses of the efficacy outcomes will be performed.

11.2.15. Interim Analyses

An interim analysis for futility may be conducted. If an interim analysis for futility is conducted, the details will be described in the SAP prior to the analysis. Only the data and safety monitoring board (DSMB) is authorized to evaluate unblinded interim efficacy and safety analyses. Study sites will receive information about interim results ONLY if they need to know for the safety of their subjects.

Unblinding details will be specified in the unblinding plan section of the SAP or a separate unblinding plan document.

12. Informed Consent, Ethical Review, and Regulatory Considerations

12.1. Informed Consent and HIPAA Compliance

12.1.1. Informed Consent

The investigator is responsible for ensuring that the subject and study partner(s) understand the potential risks and benefits of participating in the study, including answering any questions the subject may have throughout the study and sharing in a timely manner any new information that may be relevant to the subject's willingness to continue his or her participation in the trial.

The ICF will be used to explain the potential risks and benefits of study participation to the subject in simple terms before the subject is entered into the study, and to document that the subject is satisfied with his or her understanding of the risks and benefits of participating in the study and desires to participate in the study.

The investigator is responsible for ensuring that informed consent is given by each subject before the performance of any protocol procedures and before the administration of investigational product. The investigator is also responsible for ensuring that study partners provide informed consent.

As used in this protocol, the term "informed consent" includes all consent and assent given by subjects and study partners.

12.2. Ethical Review

The ATRI must approve all ICFs before they are submitted to the ERB and used at investigative sites. All ICFs must be compliant with the International Conference on Harmonisation (ICH) guideline on GCP. Standard ATRI Regulatory Affairs procedures will be followed tracking, monitoring and assisting with ERB reviews at the sites.

As part of study initiation, documentation of ERB approval of the protocol and the ICF must be provided to ATRI as part of the regulatory packages before the study may begin at the investigative sites. The standard ATRI Regulatory Approval process will be followed. The ERB(s) will review the protocol as required.

Any member of the ERB who is directly affiliated with this study as an investigator or as site personnel must abstain from the ERB's vote on the approval of the protocol.

12.3. Confidentiality

An identification code assigned by the investigator to each subject will be used in lieu of the subject's name in order to protect the subject's identity when reporting AEs and/or other trial-related data.

In addition, information about study subjects will be kept confidential and managed according to the requirements of HIPAA. Those regulations require a signed subject authorization informing the subject of the following:

- What protected health information (PHI) will be collected from subjects in this study
- Who will have access to that information and why
- Who will use or disclose that information
- The rights of a research subject to revoke their authorization for use of their PHI

In the event that a subject revokes authorization to collect or use PHI, the investigator, by regulation, retains the ability to use all information collected prior to the revocation of subject authorization. For subjects that have revoked authorization to collect or use PHI, attempts should be made to obtain permission to collect at least vital status (that is, that the subject is alive) at the end of their scheduled study period.

12.4. Inclusion of Women and Minorities

Special efforts will be made to encourage minority enrollment, with a requirement to screen at least one out of every 5 subjects from an under-represented minority, and minority recruitment will be monitored throughout the study. Minority enrollment will be facilitated through minority outreach effort coordinated by the Recruitment and Retention group at the ATRI. Each site will be encouraged to employ specific efforts (for example, media and community outreach activities) to attract appropriate minority subjects to the trial. Spanish translation is available for a variety of instruments deployed in this trial. The success of minority recruitment is based on the specific efforts of each site (for example, media and community outreach efforts) as well as the criteria for entry. This trial has been designed to maximize minority participation in both ways. No subject will be excluded due to their sex, race, or ethnic group.

12.5. Regulatory Considerations

This study will be conducted in accordance with:

- [1] consensus ethics principles derived from international ethics guidelines, including the Declaration of Helsinki and Council for International Organizations of Medical Sciences (CIOMS) International Ethical Guidelines
- [2] the ICH GCP Guideline [E6]
- [3] applicable laws and regulations

The investigator or designee will promptly submit the protocol to applicable ERB(s).

12.6. Site Personnel Requirements

12.6.1. Roles and Responsibilities

At a minimum, 3 staff members (Site Principal Investigator, Study Coordinator, Psychometrician) will be required to conduct the protocol at each site. Additional functions are

outlined below that may be covered by one staff member at certain sites; for other sites there will be multiple staff assigned. Details will be provided in the relevant procedures manual.

- Site Principal Investigator. This person is responsible for ensuring that the local ERB approves the protocol and oversees all site activity for the study; this person may also serve as the study physician. See also Section 12.6.2.
- Study Physician. This person is responsible for conducting or supervising the amyloid disclosure process, and clinical evaluation of all subjects, including physical and neurological examinations, reviewing AEs, interpreting laboratory results; ensuring enrollment and protocol adherence. The study physician will supervise project personnel and ensure that raters maintain a high level of skill and accuracy in conducting assessments.
- Study Coordinator. This person will be responsible for managing the day-to-day conduct of the trial, ensuring accurate administration of all instruments, maintaining online data and scheduling study procedures, processing laboratory samples, serving as liaison with the clinical monitor, and coordinating clinic visits. The study coordinator may perform several ratings, including the CDR.
- Rater/Psychometrician. This person will have at least 1 year experience administering cognitive assessments to older and cognitively impaired subjects.
- CDR Rater: This person must have a current rater certification through Washington University and should have at least 2 years of clinical experience in interviewing and assessing older and cognitively impaired subjects, and will render the CDR rating based on clinical judgment of study subject and study partner.
- Regulatory: This person will be responsible for managing all regulatory related documents for the duration of the trial, including submitting all required regulatory documents to ATRI regulatory affairs.
- Billing Remittance and Statement: This person will be responsible for reviewing and verifying payments from the ATRI are in alignment with procedures completed, along with accepting and processing payments from the ATRI.
- MRI Contact: This person will be responsible for conducting necessary scan for site qualification purposes using the appropriate scanning sequence. As well as conducting subject MRI scans per protocol and ensuring the scans are uploaded to the A4 portal in a timely manner.
- PET Contact: This person will be responsible for conducting necessary scan for site qualification purposes and as needed to assess for drift using the appropriate scanning sequence. As well as conducting subject PET scans per protocol and ensuring the scans are uploaded to the A4 portal in a timely manner.

